### **End of Study and Length of Study**

The approximate length of the entire study from the first patient enrolled to the last patient, last visit (LPLV; see below) is approximately 3 years. For each individual patient, the study is expected to last approximately 2 years (patients will receive 3 mg/kg/week emicizumab for the first 4 weeks followed by 1.5 mg/kg/week emicizumab for the remainder of the 2-year treatment period). *Patients who discontinue emicizumab prior to the completion of the 2-year treatment period will undergo a Safety Follow-up Visit 24 weeks after the patient's last emicizumab dose or at 2 years after emicizumab treatment start, whichever occurs first.*

The end of this study is defined as the date when the last remaining patient has completed the last visit (i.e., LPLV). The study will end when all patients have been treated with emicizumab for 2 years, or earlier, if one of the following is documented:

Withdrawal of consent

OR

Completed the Safety Follow-up Visit 24 weeks after discontinuing emicizumab

OR

Lost to follow-up

OR

Death.

### **Investigational Medicinal Products**

#### **Test Product (Investigational Drug)**

Emicizumab will be administered at a dose of 3 mg/kg/week subcutaneously for 4 weeks when initiating treatment, followed by 1.5 mg/kg/week subcutaneously for the remainder of the 2-year treatment period. There will be an option to increase the dose to 3 mg/kg/week in cases of insufficient control of bleeds on the 1.5 mg/kg/week emicizumab dose. If the investigator believes that a specific patient warrants dose up-titration following the occurrence of, for example, at least two spontaneous bleeds, significant bleeds, or a traumatic bleed out of proportion to the degree of injury, they must discuss the case with the Medical Monitor for consideration and potential approval.

To support home administration of the drug, patients/caregivers will be required to complete in-person, instructional training on how to administer emicizumab as a subcutaneous (SC) injection. Patients/caregivers will be taught to perform the injections utilizing the Instructions for Use document. *In addition, the healthcare provider (HCP) is to inform the patient/caregiver of the volumetric dose to be administered and the dosing frequency. The patients/caregivers will observe at least one SC injection performed by a HCP and will need to successfully administer at least one SC injection under an HCP's supervision prior to starting home administration. The patient/caregiver will also have the opportunity to ask any questions to the HCP before starting home administration. The first three weekly treatments will be administered in a monitored setting, such as an infusion center, clinic, or hospital, in conjunction with emicizumab PK and pharmacodynamic (PD) assessments. Patients will be observed*

for a minimum of 60 minutes after the first three doses. Patients/caregivers will be instructed on how to recognize signs/symptoms of hypersensitivity (including anaphylaxis) and obtain emergency care in the event of such reactions occurring. Each site will have the discretion to provide additional training or include additional observation (e.g., after the third or fifth doses), if deemed appropriate. If, despite additional training, the investigator determines that the patient/caregiver is unable to inject emicizumab, a trained and proficient caregiver or HCP should be identified to administer the SC injections. Patients/caregivers will be provided with contact information for the clinic in case they have questions related to self-administration between visits.

Compliance in the home setting is to be monitored at each site by reviewing reported hemophilia medication use and recording collected used and unused vials.

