**Figure 1 Study Design**

FVIII=Factor VIII; SC=subcutaneous

The primary objective of this study is to evaluate the overall safety and tolerability of prophylactic administration of emicizumab in patients with *congenital* hemophilia A who have persistent inhibitors against FVIII at enrollment. In order to achieve this objective, all adverse events, including adverse events of special interest, will be captured on an ongoing basis, as they occur during the study. Physical examinations, vital signs, and laboratory values will be assessed as per the Schedule of Activities (Appendix 1

Schedule of Activities

).

The secondary objective of this study is to evaluate the efficacy of prophylactic administration of emicizumab. As part of this objective, the number of bleeds over time will be recorded for all of the enrolled patients.

The final analysis will be conducted when all patients have completed 2 years of treatment or have withdrawn, whichever occurs sooner. Patients, or their legally authorized representative, will be asked to report bleed information on an electronic patient-reported outcome (ePRO) device where possible, including site of bleed, type of bleed, time of each individual bleed (day, start and stop time), and treatment for bleed. Health-Related Quality of Life (HRQoL) will be assessed and the EuroQoL Five-Dimension-Five Levels Questionnaire (EQ-5D-5L) will be completed prior to the first emicizumab administration (Week 1), at the Month 3, 6, 12, and 18 assessments, and at study completion as outlined in the Schedule of Activities (Appendix 1

Schedule of Activities

). Additional secondary endpoints include assessing patient preference for the emicizumab regimen compared with the previous regimen using a questionnaire (EmiPref).

Immunogenicity will be monitored by incidence and clinical significance of antibodies to emicizumab. In addition, pharmacokinetic (PK) data for emicizumab will be obtained at defined timepoints as per

the Schedule of Activities ([Appendix 1](#)  
Schedule of Activities

).

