### **3.3.7 Rationale for Disease Response–based Endpoints**

The secondary objective of this study is to evaluate the efficacy of prophylactic administration of emicizumab. This objective will be achieved by investigating the number of bleeds over time under emicizumab treatment, *assessing HRQoL, and evaluating health status according to EQ-5D-5L and patient preference for the emicizumab regimen compared with the previous regimen*. As mentioned in [Section 0](#), this analysis will occur when all patients have completed 2 years of treatment or have withdrawn, whichever occurs sooner. In order to obtain comprehensive data on each bleed, patients will be asked to report bleed information *on an ePRO device where possible*, including site of bleed, type of bleed, time of each individual bleed (day, start and stop time), and treatment for bleed.

Conducting the efficacy analysis after 2 years of therapy is supported by the results of previous clinical studies that have demonstrated the benefits of long-term prophylactic therapy in patients with hemophilia ([Gringeri et al. 2011](#); [Khawaji et al. 2012](#); [Manco-Johnson et al. 2007](#)). The results of these studies showed that prophylactic treatment could effectively prevent joint damage, decrease the frequency of joint and other hemorrhages, and lead to improvements in the patients' HRQoL.

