
Efficacy periods:

The start of the efficacy period for each individual starts on the date of first emicizumab treatment. The end of the efficacy period is defined as the date of the clinical cutoff or the date of withdrawal from/completion of the treatment whichever is earlier.

For patients who withdraw from the study before reaching the Week 1 visit, the duration of efficacy period is set to 1 day, and it starts and ends on the day of enrollment.

For patients whose dose is up-titrated, the efficacy period ends one day prior to the first day on the up-titrated dose (Efficacy period 1).

For patients whose dose is up-titrated, the bleeds occurring during the administration of the up-titrated dose are analyzed separately. The efficacy period on the up-titrated dose starts with the first day on this dose and ends on the day of the clinical cutoff or the date of withdrawal from/completion of treatment (Efficacy period 2).

For statistical evaluations (e.g. descriptive summaries) of post-baseline data summarized by visit, only measurements at scheduled visits are considered. If a measurement is repeated at a scheduled visit (or time point), then only the latest retest result will be used in calculation of the statistical summary. All data – including unscheduled measurements – will be included in the listings.

If a time interval was calculated in minutes, hours or days and needs to be converted into months or years the following conversion factors will be used:

1 year = 365.25 days

1 month = 30.4375 days

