## **4.6 EFFICACY ANALYSIS**

This is a single arm study and, consequently, no formal treatment group comparisons will be conducted.

The efficacy analyses will be based on the ITT population. Efficacy analyses will be restricted to the period before up-titration, if any, except if stated otherwise.

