#### **4.6.1.1 Bleeds**

The primary analysis will be based on treated bleeds (see definition 2.2.2.2). The number of bleeds over time will be estimated using a negative binomial (NB) regression model, which accounts for different follow-up times. The time that each patient stays in the study (efficacy period) will be included as an offset in the model.

An additional model which adjusts for number of bleeds (< 9 or ≥ 9, according to eCRF) in the last 24 weeks prior to study entry will be used to support the primary analysis.

In the rare case that the negative binomial model does not converge or no bleeds were observed for a given endpoint, the primary analysis will be based on “calculated” annualized bleed rate (ABR).

The ABR is calculated using the following formula (called Calculated ABR on all outputs):

$$\frac{\text{Number of bleeds during the efficacy period}}{\text{Number of days during efficacy period}} \times 365.25$$

The efficacy analyses will include the following endpoints defined in section 2.2.2: treated bleeds, all bleeds, treated joint bleeds, treated target joint bleeds and treated spontaneous bleeds. For each endpoint, the model based ABR will be estimated along with its corresponding 95% CI. In addition, the mean, 95% CI based on Exact Poisson, median, IQR, min and max will be provided for the calculated ABR.

A corresponding listing will be provided which will include for each patient the duration of efficacy period, number of bleeds together with calculated ABR for treated bleeds, all bleeds, treated spontaneous bleeds, treated joint bleeds and treated target joint bleeds (based on data before up-titration only). A separate listing will also be provided for the up-titrated population, based on data on or after the up-titration.

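### Efficacy summaries stop the day before up-titration, so no planned table shows bleeding over the whole emicizumab treatment period, and the later interval tables lose patients because they bled

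*Protocol*

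**What the plan says.** Protocol 4.3.2.1 and the synopsis allow up-titration, subject to discussion with and approval by the Medical Monitor: "There will be an option to increase the dose to 3 mg/kg/week in cases of insufficient control of bleeds". The study description says that "the number of bleeds over time will be recorded for all of the enrolled patients", and Protocol 3.3.7 states that the efficacy objective will be met by "investigating the number of bleeds over time under emicizumab treatment".

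SAP 4.6 says "The efficacy analyses will be based on the ITT population" and then: "Efficacy analyses will be restricted to the period before up-titration, if any, except if stated otherwise". SAP 4.1 ends Efficacy period 1 one day before the first up-titrated dose and starts Efficacy period 2 on that dose. It adds that "the bleeds occurring during the administration of the up-titrated dose are analyzed separately". The only output then specified for period 2 is in SAP 4.6.1.1: "A separate listing will also be provided for the up-titrated population, based on data on or after the up-titration".

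The negative binomial model in 4.6.1.1 uses the efficacy period as its offset. The interval summaries in 4.6.5 count only intervals that fit wholly inside that period and drop any bleed after the last full one. The categories in 4.6.1.2 include raw bleed counts. The 24-week sensitivity analysis in 4.6.6 also stops at the end of period 1. Nothing in 4.6.5 to 4.6.7 pools the two periods.

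**The concern.** Up-titration is triggered by bleeding, so the cut-off is tied to the outcome. A patient on 3 mg/kg/week is still under emicizumab treatment, but bleeds on that dose enter no rate, interval, category or sensitivity table.

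Two different things are at stake. First, a reader who sees an ITT label and a two-year treatment period may take the reported ABR as the rate over all treatment, when it is the rate before any up-titration. Second, in the summaries by calendar interval, heavy bleeders drop out of later denominators. The remaining patients bleed less, and the table can fall over time even if no one's bleeding changed.

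Elsewhere the SAP does plan for this period. Hemophilia medications (4.5) and adverse events (4.9.2) get a summary after up-titration if at least 10 patients are up-titrated. Bleeds, the reason for up-titrating, have no such rule.

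**Working it through.** The documents give no precision figure for bleeds. Their only sample-size figure, the Clopper-Pearson table for adverse events at N=200, reproduces exactly (for example 10/200: 2.4% to 9.0%) but does not bear on this point.

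**Share up-titrated.** Protocol 1.2.2.3 reports two up-titrated patients among 109 in the earlier inhibitor study. 2/109 = 1.8%, exact 95% CI 0.2% to 6.5%. For this trial, 200 × 2/109 = 3.7, about 4 patients.

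**Bleed model.** From the same study, treated-bleed ABR is 2.9 and 62.9% had no treated bleed. Take each patient's rate as gamma with mean 2.9 and shape k, with Poisson counts. Then P(0) = (1 + μ/k)^(−k). At an assumed 24 weeks, μ = 2.9 × 24/52.18 = 1.33, and P(0) = 0.629 gives k = 0.25.

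**Assumptions not in the documents.** N = 200, all followed for 2 years. A patient qualifies after two treated bleeds within 24 weeks. The approval probability is varied to give about 2%, 4% or 10% up-titrated. The bleed rate after up-titration is multiplied by 1.0, 0.5 or 0.2.

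**Negative binomial ABR** (100 replicates per cell), SAP cut versus the whole 2 years:

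| Up-titrated | Ratio 1.0 | Ratio 0.5 | Ratio 0.2 |
|---|---|---|---|
| about 2% | 2.88 vs 2.88 | 2.92 vs 2.85 | 2.90 vs 2.80 |
| about 4% | 2.96 vs 2.95 | 2.93 vs 2.78 | 2.86 vs 2.62 |
| about 10% | 2.96 vs 2.95 | 2.83 vs 2.48 | 2.90 vs 2.32 |

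The SAP estimate stays near the assumed 2.9 throughout, so it recovers the rate without up-titration. The gap to the whole-period rate is 0.0 to 0.1 at 2% and 0.0 to 0.6 at 10%.

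**Weeks 73–96 mean ABR under SAP 4.6.5** (600 replicates per cell; bleeds in the interval / 168 × 365.25), SAP rule versus all patients:

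| Up-titrated | Ratio 1.0 | Ratio 0.5 | Ratio 0.2 |
|---|---|---|---|
| about 2% | 2.65 vs 2.87 | 2.67 vs 2.78 | 2.69 vs 2.73 |
| about 4% | 2.39 vs 2.91 | 2.41 vs 2.64 | 2.41 vs 2.50 |
| about 10% | 1.80 vs 2.91 | 1.79 vs 2.34 | 1.76 vs 1.97 |

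The two outputs err in opposite directions. The cut negative binomial ABR lies above the whole-period rate, most when up-titration works. The cut interval mean lies below it, most when up-titration does nothing. In that last case the true rate is flat at 2.9, yet at 10% up-titrated the table would show 1.8. About 30% of up-titrated patients' earlier bleeds also fell in a discarded partial interval.

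**Count categories (4.6.1.2).** A patient up-titrated soon after a second bleed stays in the 1–3 group whatever follows. With no benefit from up-titration, the share with more than 10 treated bleeds was 16.2% under the SAP rule against 16.7% at 2% up-titrated, and 13.3% against 17.0% at 10%.

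**The case against.** The case for leaving the SAP alone has real force.

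- Protocol 3.3.1 names 3 mg/kg weekly for 4 weeks followed by 1.5 mg/kg weekly as the regimen to be investigated. Up-titration is a case-by-case option. A reader might infer that the rate on the regimen tested is never estimated. The documents do not support that: the pre-up-titration ABR estimates the rate on the regimen that 3.3.1 names.
- The cut is deliberate. The SAP history says the efficacy period was aligned with two sister emicizumab studies. That is a good reason to keep the analysis, but not a reason to have no other.
- Bleeds after up-titration are not thrown away. SAP 4.1 defines period 2, and 4.6.1.1 lists those patients. If that listing carries period length and bleed count, a reader could add the periods by hand. With about four patients this may suffice for the ABR. It does not repair the interval or category tables.
- Efficacy is secondary and everything is descriptive, so no error rate or primary safety conclusion is affected.

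A reader might also infer that late HRQoL means look too good. The documents do not support a direction: if up-titration works, the excluded forms need not be worse, and no score gap is given anywhere. The comparison that Protocol 6.5 names is at 6 months, which later up-titrations do not touch.

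**Conclusion.** The gap is real but moderate. It is an unlabelled choice of question for the main ABR, not a biased fit. The distortion lies in the 4.6.5 interval summaries and, less so, in the 4.6.1.2 count categories.

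At about 2% up-titrated, the negative binomial ABR moves by 0.0 to 0.1 and the weeks 73–96 mean by about 0.1 to 0.2 if the rate is unchanged or halved after up-titration. At an assumed 10% the figures are 0.0 to 0.6 and about 0.6 to 1.1. With a rate cut to one fifth, the interval gap shrinks to under 0.1 and about 0.2.

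These sizes rest on the assumed trigger, bleed distribution and response. The share in this trial is unknown. The earlier study allowed up-titration only after 24 weeks, while the criteria here are given as examples with no such wait, so a higher share is possible but not documented. The finding that the negative binomial model holds up also assumes that the trigger depends only on the bleeds being modelled.

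**What to change.** Keep the pre-up-titration analysis and label it as the rate on the 1.5 mg/kg maintenance regimen, before any up-titration. In SAP 4.6.6 add the same negative binomial model for all five bleed endpoints over the full treatment period regardless of up-titration, with the offset equal to full treatment time. Repeat the 4.6.5 interval and 4.6.1.2 category summaries on that period and show them beside the present ones.

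For HRQoL (4.6.2) and EQ-5D-5L (4.6.3), add by-visit summaries that include forms completed after up-titration, as a sensitivity analysis with no stated expectation about direction.

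The cost is SAP wording and one extra set of tables. No new data are needed, and no change to dosing or to the up-titration criteria is proposed. If few patients are up-titrated, the two sets should largely agree and show that the results are robust.

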## **Statistical Methods**

### **Primary Safety Analyses**

The primary objective of this study is to evaluate the overall safety and tolerability of prophylactic administration of emicizumab in patients with *congenital* hemophilia A who have *persistent* inhibitors against FVIII at enrollment. Of primary interest in this study are the incidence and severity of *all* adverse events, including thromboembolic *events*, *microangiopathic hemolytic anemia* or TMA, systemic hypersensitivity, anaphylaxis, and anaphylactoid events.

All adverse events will be assessed according to the World Health Organization (WHO) toxicity grading scale. The incidence, type, and grade of adverse events will be summarized according to the primary system-organ class (SOC) and, within each SOC, by Medical Dictionary for Regulatory Activities (MedDRA) preferred term. For each adverse event, data will be provided on the timing (start and stop date, time of onset in comparison with last dose of emicizumab received, and doses of emicizumab received), severity, relationship to *emicizumab*, outcome, and effect on therapy. The data may be presented together with two-sided 95% Clopper-Pearson confidence intervals (CIs) if appropriate.

In addition, as part of the safety evaluation, additional assessments will be summarized descriptively as follows:

1. Cumulative *emicizumab* doses, dose modifications (delays and interruptions), and duration of exposure
2. Compliance with respect to emicizumab intake (planned vs. received)
3. Changes from baseline in physical examination findings
4. Vital signs over time:
  - Vital signs will be analyzed using descriptive statistics for continuous variables and presented graphically over time with associated 95% CIs.
5. Laboratory parameters (hematology and chemistry):
  - These parameters will be presented in shift tables of WHO toxicity grade at baseline versus worst grade during the treatment period. Selected laboratory parameters will be summarized in terms of mean, standard deviation, minimum, and maximum. Laboratory parameters will also be presented graphically over time.

All safety variables will be analyzed for the safety population. For each variable, the number of available observations will be reported. The safety population includes all patients who have received at least one dose of *emicizumab*.

The primary safety analysis will occur at the end of the study.

*The iDMC will evaluate the study data, including the emerging safety results, at periodic reviews and recommend to the Sponsor whether the protocol should be amended or the study should be stopped early. All summaries and analyses will be prepared by the Study Management Team (SMT) statistician and presented for iDMC review. Members of the iDMC will be external to the Sponsor and will follow a charter that outlines their roles and responsibilities.*

A detailed description of the statistical methods that will be used for the primary and secondary analyses will be provided in the Statistical Analysis Plan (SAP).

**Determination of Sample Size**

A sample size of approximately 200 patients is planned for this study.

For the purpose of the sample size calculation, the incidence of adverse events was chosen as the safety endpoint of primary interest.

If the observed incidence of adverse events is between 2.5% and 15%, the precision for the estimated incidence rate is presented below according to the 95% Clopper-Pearson CIs ([Table 2](#)).

**Table 2 Clopper-Pearson 95% CIs for the Incidence of AEs (Based on N=200)**

Number of AE Events (Observed AE Incidence)	95% Clopper-Pearson CIs
5 (2.5%)	0.8%–5.7%
10 (5.0%)	2.4%–9.0%
20 (10.0%)	6.2%–15.0%
30 (15.0%)	10.4%–20.7%

AE=adverse event, CI=confidence interval

### **Interim Analyses**

The first *interim* analysis will be performed once *approximately* 100 patients have received treatment with emicizumab for at least 24 weeks. A second *interim* analysis will be performed when *approximately* 100 patients have received treatment with emicizumab for at least 52 weeks. The data from these analyses will subsequently be presented to an iDMC in order to enable them to effectively monitor the study.

Details regarding the planned interim analyses will be provided in the SAP and iDMC charter.

## LIST OF ABBREVIATIONS AND DEFINITIONS OF TERMS

Abbreviation	Definition
ABR	annualized bleeding rate
ADA	anti-drug antibody
ALT	alanine aminotransferase
aPCC	activated prothrombin complex concentrate
aPTT	activated partial thromboplastin time
AST	aspartate aminotransferase
AUC	area under the curve
AUC T	area under the curve during the dosage interval
BU	Bethesda unit
BUN	blood urea nitrogen
CI	confidence interval
C max	maximum plasma concentration
CONSORT	Consolidated Standards of Reporting Trials
CRO	contract research organization
C trough	concentration at the end of the dosage interval
CTX	C-terminal telopeptide of collagen 1
CVAD	central venous access device
CWA	clot waveform analysis
cyFcγR	cynomolgus monkey Fcγ receptor
EC	Ethics Committee
ECG	electrocardiogram
ECL	electrochemiluminescence
eCRF	electronic Case Report Form
EDC	electronic data capture
EDTA	ethylenediaminetetraacetic acid
ELISA	enzyme linked immunosorbent assay
ePRO	electronic patient-reported outcome
EQ-5D-5L	EuroQoL Five-Dimension-Five Levels Questionnaire
EQ-VAS	EuroQoL visual analogue scale
E.U.	European Union
FDA	Food and Drug Administration
FEIBA	Factor eight inhibitor bypassing activity
FIX	Factor IX
FIXa	activated Factor IX
FIX:Ag	Factor IX antigen
FVIIa	activated Factor VII

Abbreviation	Definition
FVIII	Factor VIII
FVIII:Ag	Factor VIII antigen
FX	Factor X
FX:Ag	Factor X antigen
Haem-A-QoL	Hemophilia Adult Quality of Life Questionnaire
Haemo-QoL	Hemophilia Quality of Life
Haemo-QoL-SF	Hemophilia Quality of Life Short Form
HCP	healthcare provider
hFcyR	human Fcy receptor
HIV	human immunodeficiency virus
HRQoL	Health-Related Quality of Life
ICH	International Conference on Harmonisation
iDMC	independent Data Monitoring Committee
IFU	Instructions for Use
IgE	immunoglobulin E
IgG	immunoglobulin G
IMP	investigational medicinal product
IND	Investigational New Drug
INR	international normalized ratio
IRB	Institutional Review Board
ISTH	International Society on Thrombosis and Haemostasis
ITI	immune tolerance induction
ITT	intent-to-treat
IV	intravenous
IxRS	interactive voice or web-based response system
LDH	lactate dehydrogenase
LPLV	last patient, last visit
MABEL	minimal anticipated biological effect level
MAD	multiple ascending dose
MedDRA	Medical Dictionary for Regulatory Activities
NIS	non-interventional study
NOAEL	no observed adverse effect level
OPG	osteoprotegerin
P1NP	procollagen type 1 amino-terminal propeptide
PD	pharmacodynamic(s)
pdFVIII	plasma-derived Factor VIII
PK	pharmacokinetic(s)
PRO	patient-reported outcome

Abbreviation	Definition
PT	prothrombin time
RANK-L	receptor activator of nuclear factor kappa-B ligand
RBC	red blood cell
rFVIIa	recombinant activated human Factor VII
rFVIII	recombinant Factor VIII
SAD	single ascending dose
SAP	Statistical Analysis Plan
SC	subcutaneous
SMT	Study Management Team
SOC	system-organ class
SSC	Scientific and Standardization Committee
$t_{1/2}$	terminal plasma half-life
TMA	thrombotic microangiopathy
$t_{max}$	time to maximum plasma concentration
ULN	upper limit of normal
U.S.	United States
VAS	visual analog scale
$V_{ss}$	volume of distribution at steady state
WBC	white blood cell
WHO	World Health Organization

